20.2 Ethical Conduct of the Study

The procedures set out in this clinical trial protocol pertaining to the conduct, evaluation, and documentation of this clinical trial, are designed to ensure that the Sponsor and Principal Investigator abide by Good Clinical Practice Guidelines (GCP). The clinical trial will also be carried out in accordance with applicable local law(s) and regulation(s).

20.3 Written Informed Consent

An information and consent form will be provided to the subject. The process of obtaining informed consent must be in accordance with applicable regulatory requirements and must adhere to GCP and ethical principles in the Declaration of Helsinki. Written informed consent must be obtained and documented before any clinical trial-specific procedure takes place. Participation in the clinical trial and date of informed consent given by the subject must be documented in the subject files.

1 INTRODUCTION

This Statistical Analysis Plan (SAP) describes the planned analysis and reporting MediciNova Inc. protocol MN-166-COVID-19-201, *A Randomized, Double-Blind, Placebo-Controlled, Parallel Group Study to Evaluate the Efficacy, Safety, Tolerability, Biomarkers and PK of ibudilast (MN-166) in COVID-19 Participants at Risk for Developing Acute Respiratory Distress Syndrome.*

This phase 2 study is being completed to assess the safety, tolerability, and efficacy of MN-166 in male and female subjects 18 to 80 years of age, inclusive, who are hospitalized for complications from COVID-19 infection, are at risk for developing ARDS, and receive standard of care including anticoagulation. The following documents were reviewed in preparation of this SAP:

- Clinical Study Protocol MN-166-COVID-19-201, amendment 2 issued 01 November 2021 and amendment 4 issued 31 March 2021*
- Case report forms (CRFs) for Protocol MN-166-COVID-19-201.
- ICH E9: Guidance on Statistical Principles for Clinical Trials.
- ICH E3: Guideline for the format and content of the clinical and statistical sections of an application
- ICH E14: Clinical evaluation of QT/QTc interval prolongation and proarrhythmic potential for non-antiarrhythmic drugs

The SAP supplements the clinical protocol. Please refer to the clinical protocol for details on the rationale for the intervention, eligibility criteria, conduct of the trial, clinical assessments and the timing of their use in the trial, definitions and reporting of adverse events, data management conventions, and regulatory oversight and compliance procedures. In case of discrepancies between the SAP and the clinical protocol concerning matters of data analysis, the SAP is authoritative. On all other matters, the clinical protocol is authoritative.

**No subjects were consented under Protocol v.1.0, Amendment 1, and Amendment 3 because they were not submitted to the institutions' IRB.*

2 STUDY OBJECTIVE AND ENDPOINTS

2.1 Study Objectives

2.1.1 Primary objectives

The primary objectives of the study are to evaluate:

- Efficacy of ibudilast vs. placebo in COVID-19 subjects measured by the proportion of subjects free of respiratory failure at Day 7
- Efficacy of ibudilast vs. placebo in COVID-19 subjects measured by clinical status at Day 7

2.1.2 Secondary Objectives

The secondary objectives of the study are to evaluate:

Confidential

- Efficacy of ibudilast vs. placebo in COVID-19 subjects measured by the proportion of subjects free of respiratory failure at Days 14, 28 and 60 (in intubated subjects only)
- Efficacy of ibudilast vs. placebo in COVID-19 subjects measured by clinical status at Days 14, 28 and Day 60 (in intubated subjects only)
- Anti-inflammatory effects of ibudilast vs. placebo on cytokine levels
- Safety and tolerability of ibudilast vs. placebo in COVID-19 subjects
- Pharmacokinetics of ibudilast vs. placebo in COVID-19 subjects

2.2 Study Endpoints (Outcome Variables)

2.2.1 Co-Primary Outcome Variable(s)

The co-primary objectives of the study will be evaluated based on the following clinical measures:

- Proportion of subjects free from respiratory failure defined by free from supplemental oxygen requirements (invasive mechanical ventilation, non-invasive ventilation, high-flow oxygen, or ECMO, CPAP, BiPAP, nasal cannula) at Day 7
- Proportion of subjects with at least a one-point improvement in clinical status using the NIAID 8-point ordinal scale and discharge record at Day 7

2.2.2 Secondary Outcome Variable(s)

- Proportion of subjects free from respiratory failure as defined by free from supplemental oxygen requirement (invasive mechanical ventilation, non-invasive ventilation, high-flow oxygen, or ECMO, CPAP, BiPAP, nasal cannula) at Days 14, 28 and Day 60*
- Proportion of subjects with mechanical ventilation /intubation at Days 7, 14, 28 and Day 60*
- Changes from baseline in clinical status using the NIAID 8-point ordinal scale and discharged record at Days 7, 14, 28 and 60*
- Proportion of subjects with at least a one-point improvement in clinical status using the NIAID 8-point ordinal scale and discharge record at Days 14, 28 and 60*
- All-cause mortality at Days 28 and Day 60*
- Proportion of the subjects discharged from hospital at Days 7, 14, 28 and 60*
- Change from baseline in migration inhibitory factor (MIF), (interleukin 1-beta (IL-1 β), interleukin 6 (IL-6), tumor necrosis factor (TNF- α), and C-reactive protein (CRP) at Day 3,5,7 and 14
- Incidence, frequency, and severity of adverse events at Day 7, 14, 28 and Day 60*
- Change from baseline of the following parameters at Days 7, 14 and Day 60*:
 - o ALT
 - o AST

Confidential

- o Serum creatinine
- o BUN
- o Complete blood count
- o Total bilirubin
- o D-dimer
- PK plasma concentrations and parameter (PK population)

*Intubated subjects only on Study Day 60

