16.5 Recording Adverse Events

Adverse events should be collected and recorded for each subject from the date the patient receives study drug until the end of their participation in the study, (i.e., the subject has discontinued or completed the study) through the follow-up visit.

Adverse events may be volunteered spontaneously by the study subject, or discovered by the study staff during physical examinations or by asking an open, non-leading question such as, "How have you been feeling since you were last asked?" All AEs and any required remedial action will be recorded in the subject's source documentation and transcribed onto the appropriate CRF page for the study period indicated. The nature of AE, date (and time, if known) of AE onset, date (and time, if known) of AE outcome to date, severity, and action taken of the AE will be documented together with the PI's or an authorized physician's assessment of the

seriousness of the AE and causal relationship to study medication and/or study procedure (at the time of assessment).

All AEs should be recorded individually in the study subject's own words (verbatim) unless, in the opinion of the PI or an authorized physician, the AEs constitute components of a recognized condition, disease, or syndrome. In the latter case, the condition, disease, or syndrome should be named rather than each individual symptom. The AEs will subsequently be coded using the most current version of MedDRA.

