3 STUDY METHODS AND ENDPOINTS

3.1 Overall Study Design and Plan

This is a randomized (1:1), placebo-controlled, double-blind, parallel-group study of MN-166 (ibudilast) in hospitalized COVID-19 subjects at risk for developing ARDS receiving standard of care including anticoagulation. Approximately 40 participants are planned to be enrolled. The study will consist of a Screening Phase followed by a 7-days Double-blind Treatment (DBT) and Follow-up Phase. Following the Screening Phase, if the subject meets eligibility criteria, subject will be administered treatment with MN-166 (ibudilast) or placebo. Subjects will receive ibudilast 100 mg/d (50 mg b.i.d) or placebo every day for 7 days. The Follow-up phase is consisted of three visits: Day 14, Day 28, and Day 60 (subjects enrolled under amendment 4 only) post-baseline visit.

Subjects who are discharged prior to Day 7 will be given the remainder of their study medication to be taken at home and a pulse oximeter supplied by the sponsor to measure their O₂ levels once daily until Study Day 14.

Eligible participants will consist of males and females ranging in age from 21 to 80 years old, inclusive, who have SARS-CoV-2 infection confirmed by WHO criteria, chest abnormalities consistent with COVID-19 pneumonia, SpO₂ ≤92% on room air, ≥24 BPM, and/or requirement of supplemental O₂.

Overall study design and plan is described in detail in Protocol Section 11.

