6.1 Use of analysis populations in different analyses

Safety analyses will be conducted on the Safety Analysis Set, and participants will be analyzed based on the treatment they received. Efficacy analysis will be conducted on the Full Analysis Set, and participants will be analyzed based on the treatment to which they were randomly assigned.

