13 APPENDICES

13.1 Schedule of Assessments (Amendment 2)

Phase	Screening	Double-Blind Treatment Phase ^{d,f}							Follow-up	
		Day -3	Day 1 BL	Day 2	Day 3	Day 4	Day 5	Day 6	Day 7	Day 14 ^d (± 3)
Study Day										
Informed consent	X									
Inclusion/exclusion criteria review	X									
Brief physical exam	X	X		X		X		X	X	
Clinical status using NIAID scale	X	X	X	X	X	X	X	X	X	X
Vital signs (BP, RR, HR, Temp)	X	X	X	X	X	X	X	X	X	
O₂ therapy status and SpO₂	X	X	X	X	X	X	X	X	X	
12-lead ECG	X	X^a		X^a		X^a		X^a		
Biomarker plasma samples: MIF, IL-1β, IL-6, TNF-α	X	X		X		X		X	X	
PK blood sample^b		X		X		X				
CBC, CMP, CRP, D-dimer, PT, INR	X^c	X		X		X		X	X	
Randomize^e	X									
Administer study drug		X	X	X	X	X	X	X	X	
Adverse event review		X	X	X	X	X	X	X	X	
Prior/Concomitant medication review	X	X	X	X	X	X	X	X	X	
Record survival status										X

^a 12-lead ECG to be done between 2-4 hours after AM dose.

^b Collect PK samples on Day 1 in the AM prior to study drug dosing and at 2, 4, 8, and 12 hours (Predose of PM dose); Day 3 and Day 5 prior to AM study drug dosing. PK samples to be collected for 8 subjects only.

^c Serum β-hCG for pre-menopausal women.

^d Telephone follow-up if subject is not in hospital. If subject is no longer hospitalized or cannot return due to COVID restrictions, a telephone follow-up to record O₂ usage/levels, AEs and conmeds may be conducted. All other assessments are optional.

^e Subjects may be randomized during the Screening Phase after all of the screening assessments are completed and subject is considered eligible for the study or on Day 1.

^f If subject prematurely discontinues from the study or is discharged from the hospital on Days 2, 4, or 6 collect biomarker samples in addition to other scheduled assessments. If subject prematurely discontinues from the study or is discharged on Days 1, 3, 5, or 7, conduct the study assessments scheduled on those days.

^gThirty-one (31) subjects were consented under Protocol amendment 2.

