13.2 Schedule of Assessments (Amendment 4)

Phase	Screening	Double-Blind Treatment Phase ^{e,g}							Follow-up		
		Day 1 BL	Day 2	Day 3	Day 4	Day 5	Day 6	Day 7	Day 14 ^c (± 3)	Day 28 (±3)	Day 60 (±7)
Study Day	Day -3										
Informed consent	X										
Inclusion/exclusion criteria review	X										
Brief physical exam	X	X		X		X		X	X		
Clinical status using NIAID scale	X	X	X	X	X	X	X	X	X	X	X
Vital signs (BP, RR, HR, Temp)	X	X	X	X	X	X	X	X	X		X ⁱ
O₂ therapy status and SpO₂	X	X	X	X	X	X	X	X	X	X	X
12-lead ECG	X	X ^a		X ^a		X ^a		X ^a			X ⁱ
Biomarker plasma samples: MIF, IL-1β, IL-6, TNF-α	X ^b	X		X		X		X	X		
PK blood sample^c		X		X		X					
CBC, CMP, CRP, D-dimer, PT, INR	X ^d	X		X		X		X	X		X ⁱ
Randomize^f	X										
Administer study drug		X ^h	X	X	X	X	X	X			
Adverse event review		X	X	X	X	X	X	X	X	X	X
Prior/Concomitant medication review	X	X	X	X	X	X	X	X	X	X	X
Record survival status^j									X	X	X

^a 12-lead ECG to be done between 2-4 hours after AM dose.

^b Biomarker blood sample collection at screening is optional if Screening and Day 1 assessments occur on the same day.

^c Collect PK samples on Day 1 in the AM prior to study drug dosing and at 2, 4, 8, and 12 hours (Predose of PM dose); Day 3 and Day 5 prior to AM study drug dosing. PK samples to be collected for 8 subjects only.

^d Serum β-hCG for pre-menopausal women.

^e Telephone follow-up if subject is not in hospital. If subject is no longer hospitalized or cannot return due to COVID restrictions, a telephone follow-up to record O₂ usage/levels, AEs and conmeds may be conducted. All other assessments are optional.

^f Subjects may be randomized during the Screening Phase after all of the screening assessments are completed and subject is considered eligible for the study or on Day 1.

^g If subject prematurely discontinues from the study or is discharged from the hospital on Days 2, 4, or 6 collect biomarkers samples in addition to other scheduled assessments. If subject prematurely discontinues from the study or is discharged on Days 1, 3, 5, or 7, conduct the study assessments scheduled on those days.

^h The first dose of study drug may be started in the AM or the PM.

ⁱ Vital signs, ECG and safety labs will be done in intubated subjects only.

Survival status is captured on the NIAID questionnaire.

^j Five (5) subjects were consented under Amendment 4.

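### Day 28 AE incidence is planned on the whole Safety Analysis Set, although the schedule for 31 of 36 consented subjects marks no AE review after Day 14

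*Combined protocol and SAP*

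**What the plan says.** SAP 2.2.2 names "Incidence, frequency, and severity of adverse events at Day 7, 14, 28 and Day 60" as a secondary outcome. Only Day 60 carries an asterisk, which leads to the footnote "Intubated subjects only on Study Day 60". SAP 3.1 also limits that visit: "Day 60 (subjects enrolled under amendment 4 only". Day 28 has no restriction of either kind.

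On the denominator, SAP 6.1 states: "Safety analyses will be conducted on the Safety Analysis Set". SAP 6 admits to that set any randomized subject with at least one dose and one post-dose safety assessment. SAP 11.1 has rules for partial onset dates, missing severity and missing relationship. It has none for a subject who had no AE review in the period being summarised.

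The SAP appendix gives two visit schedules. Under Amendment 2 (SAP 13.1, 31 consented), the row "Adverse event review" is marked on Days 1 to 7 and Day 14 and is blank in the last follow-up column. There only the NIAID status and the row "Record survival status" are marked. Under Amendment 4 (SAP 13.2), AE review is also marked at Days 28 and 60, and "Five (5) subjects were consented under Amendment 4".

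**The concern.** An incidence taken over the whole Safety Analysis Set treats a subject without a recorded event as a subject without an event. That is fair only while everyone is being asked. After Day 14 most subjects had no scheduled AE review, so a low late rate could reflect absent questioning as much as absent events.

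Two outputs are exposed: the Day 28 item in SAP 2.2.2, and Table 14.3.1.3 (post-treatment AEs), for which SAP 11.1 gives no definition, window or denominator. A reader of either could take from it a reassurance about late safety that the data cannot give. Randomization is stratified by IL-6 antibody use (protocol 15.2), not by amendment, so the arms need not hold equal shares of subjects with late review.

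**Working it through.** The documents state no AE rate, event count or power for this outcome, so there is no figure of the plan's own to reproduce.

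1. **Reading the Amendment 2 schedule.** Each row has ten cells: Screening, Days 1 to 7, Day 14 and a last follow-up column. That column's heading is lost in extraction and is taken as Day 28.
   - NIAID: ten marks.
   - Vital signs, oxygen and concomitant medication: nine marks, last cell blank.
   - AE review: Screening blank, eight marks, last cell blank.
   - Survival: last cell only.

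   In Amendment 4 the AE row has ten marks (Days 1 to 7, 14, 28 and 60).

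2. **Share without a scheduled late review.** 31 + 5 = 36 consented; 31/36 = 86.1% without and 5/36 = 13.9% with. The number dosed is not given. If 0 to 15 of the 31 and 0 to 2 of the 5 were screen failures (assumed), the share with late review runs from 3/34 = 9% to 5/21 = 24%.

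3. **New-onset events after Day 14.** Let c be the share of late AEs in Amendment 2 subjects that is recorded anyway, and assume the same true rate under both amendments. Then observed rate / true rate = (5 + 31c)/36.
   - c = 0: 5/36 = 0.14
   - c = 0.25: 12.75/36 = 0.35
   - c = 0.50: 20.5/36 = 0.57
   - c = 0.75: 28.25/36 = 0.78

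   With c = 0, assumed true late rates of 10%, 20% and 30% would appear as 1.4%, 2.8% and 4.2%.

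4. **Cumulative incidence to Day 28.** Let q be the proportion with an AE by Day 14 and p the proportion of the rest with a first AE later. The true value is q + (1 − q)p. With c = 0 the observed value is q + (1 − q)p × 5/36. For assumed q = 50% and p = 20%, the true value is 60.0% and the observed value 50% + 1.4% = 51.4%. Over q from 30% to 70% and p from 5% to 30%, the shortfall is 1 to 18 percentage points.

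5. **TEAE tables.** SAP 11.1 closes the TEAE window 7 days after the last dose. With a last dose on Day 7, or on Day 8 in the morning (protocol 13.0), the window ends on Day 14 or Day 15. The Day 14 review covers this under both schedules, except for the last days when the visit (±3 days) falls early.

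6. **Precision after restriction.** Among five subjects, the chance of seeing at least one late AE is 1 − 0.9^5 = 0.41 at a 10% rate and 1 − 0.8^5 = 0.67 at 20%. If none of five has one, the upper 95% limit is 1 − 0.025^(1/5) = 52%.

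**The case against.** The strongest reply is that AE collection is not confined to ticked visits. Protocol 16.5 says "Adverse events should be collected and recorded for each subject from the date the patient receives study drug until the end of their participation", and protocol 16.0 says much the same, so some late events in Amendment 2 subjects may well be on record. This stands in part. It is Amendment 4 text, and the Amendment 2 protocol text is not available here. It makes zero capture a worst case, but it does not put unscheduled reporting on the same footing as a scheduled review.

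The schedule itself is also open to doubt. In the extracted Amendment 2 table the study-drug row has eight marks in the same positions as the AE row, which would put a dosing mark at Day 14 in a 7-day treatment phase. At least one row therefore needs checking against the source. The vital-sign, oxygen and concomitant-medication rows also end one cell early, which makes the reading of the AE row plausible though not certain.

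A reader might infer that Day 60 has the same fault. The documents do not support that: SAP 2.2.2 limits Day 60 to intubated subjects and SAP 3.1 limits the visit to Amendment 4. A reader might also infer that AE reporting as a whole is understated about sevenfold. That does not follow either. The factor applies only to new-onset late events with nothing captured outside scheduled reviews, and the list of tables has no AE table by Day 28 or Day 60.

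**Conclusion.** The concern holds for AEs with onset after Day 14, as they enter the Day 28 item and Table 14.3.1.3. On the full denominator these rates would be biased downward, to about 14% of the true rate with no capture outside scheduled reviews and about 57% with half captured. Cumulative incidence to Day 28 suffers much less, and the TEAE tables and the Day 60 item are essentially unaffected.

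This rests on four assumptions: the Amendment 2 marks are as extracted; the 31 to 5 split among consented subjects roughly carries over to those dosed; the true late rate is similar under both amendments; and subjects without a late review stay in the denominator as event-free. The SAP does not state the last of these, but it follows from its only safety denominator. The point merits correction before reporting; it is not a failure of the trial's main safety summary.

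**What to change.** First check the Amendment 2 marks against the source table. Then change SAP 2.2.2, SAP 11.1 and the specification of Table 14.3.1.3 as follows:

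- Make AE incidence through Day 14 the safety summary for all treated subjects.
- Report AEs with onset after Day 14 separately and descriptively. Calculate the rate among subjects who had an AE review at that visit, and show that denominator by arm and amendment.
- List and count every late AE or SAE recorded in the other subjects, with a note that no AE review was scheduled for them after Day 14. Restricting the rate must not remove recorded events from the report.

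Mortality at Day 28 needs no change, since SAP 10.2 and Table 14.2.8 already cover it.

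The cost is SAP wording, denominators and one footnote; no new data are needed. The downside is that the Day 28 rate rests on about five subjects across both arms and is imprecise, as the upper limit of 52% for no events in five shows.

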6 ANALYSIS POPULATIONS

The following analysis populations are planned for the studies:

- **Full Analysis Set (FAS)** will include all randomized subjects.
- **Safety Analysis Set (SAS)** will include all randomized subjects who received at least one dose of study drug and had at least one post-dose safety assessment.
- **Per Protocol Analysis (PP):** will consist of the FAS subjects excluding those with major protocol violations.

Confidential

- **Pharmacokinetic Population (PK):** will consist of the subjects for which PK collection was performed. Eight subjects are anticipated to participate in PK sample collection.

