7.8 Clinical Status Scale

In this trial, the National Institute of Allergy and Infectious Diseases (NIAID) 8-point ordinal scale is utilized to assess clinical status at Screening, Days 1-7, and on Days 14, 28, and 60 (for intubated subjects only). In Section 14.5 of the protocol, the numbers (1-8) are in reverse, where a higher number represents improvement, which is inconsistent with the official NIAID 8-point ordinal scale. The SAS programmer will correct the NIAID 8-point ordinal scale to reflect the official scale shown below.

1. Not hospitalized, no limitations on activities
2. Not hospitalized, limitation on activities and/or requiring home oxygen
3. Hospitalized, not requiring supplemental oxygen - no longer requires ongoing medical care
4. Hospitalized, not requiring supplemental oxygen - requiring ongoing medical care (COVID-19 related or otherwise)
5. Hospitalized, requiring supplemental oxygen
6. Hospitalized, on non-invasive ventilation or high flow oxygen devices
7. Hospitalized, on invasive mechanical ventilation or extracorporeal membrane oxygenation (ECMO)
8. Death

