10.2 Secondary Efficacy Variable Analysis

The secondary efficacy endpoints are the following:

- Proportion of subjects free from respiratory failure as defined by free from supplemental oxygen requirement (invasive mechanical ventilation, non-invasive ventilation, high-flow oxygen, or ECMO, CPAP, BiPAP, nasal cannula) at Days 14, 28 and Day 60* Proportion of subjects with mechanical ventilation /intubation at Days 7, 14, 28 and Day 60*
- Change from baseline in clinical status using NIAID 8-point scale and discharge record at Days 7, 14, 28 and 60* Proportion of subjects with at least a one-point improvement in clinical status using the NIAID 8-point ordinal scale and discharge record at Day 14, 28 and 60*
- All-cause mortality at Days 28 and Day 60* Proportion of the subjects discharged from hospital at Day 7, 14, 28 and 60*
- Change from baseline in migration inhibitory factor (MIF), (interleukin 1-beta (IL-1 β), interleukin 6 (IL-6), tumor necrosis factor (TNF- α), and C-reactive protein (CRP) at Day 3, 5, 7 and 14

*Intubated subjects only on Study Day 60

All secondary endpoints that are defined as proportion variables will be analyzed using Pearson's chi-square tests. Secondary endpoints that are defined as the change from baseline will be analyzed using analysis of covariance (ANCOVA) models with treatment group as a factor and the baseline value of the corresponding endpoint as a covariate. All secondary analyses will be conducted using one-sided tests at the alpha=0.025 level of significance, with no adjustments for multiplicity.

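### The SAP restricts Day 60 efficacy, mortality, discharge and adverse-event endpoints to intubated subjects, although the protocol and the SAP's own schedule restrict only Day 60 vital signs, ECG and laboratory tests

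*Combined protocol and SAP*

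**What the plan says.** SAP 2.2.2 marks the Day 60 time point of eight secondary items with an asterisk, explained as "Intubated subjects only on Study Day 60". Six are efficacy endpoints: freedom from supplemental oxygen, mechanical ventilation or intubation, change in NIAID status, one-point NIAID improvement, all-cause mortality and hospital discharge. The other two are adverse events and the safety laboratory changes.

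The limit recurs in three places, with differing scope:

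- SAP 2.1.2 applies it to the respiratory-failure and clinical-status objectives, the latter worded "Efficacy of ibudilast vs. placebo in COVID-19 subjects measured by clinical status at Days 14, 28 and Day 60 (in intubated subjects only").
- SAP 7.8 applies it to the NIAID assessment: "and on Days 14, 28, and 60 (for intubated subjects only").
- SAP 10.2 repeats the asterisks and the footnote for the six efficacy endpoints, and adds "All secondary analyses will be conducted using one-sided tests at the alpha=0.025 level of significance, with no adjustments for multiplicity".

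The SAP's Amendment 4 schedule (13.2) is narrower. Its footnote reads "Vital signs, ECG and safety labs will be done in intubated subjects only", and the Day 60 entries for NIAID status, oxygen status, adverse events and survival carry no such mark. SAP 6 says the Full Analysis Set "will include all randomized subjects", and SAP 6.1 assigns efficacy analysis to that set. SAP 3.1 gives a Day 60 visit only to some subjects, "Day 60 (subjects enrolled under amendment 4 only"), and SAP 13.2 notes that "Five (5) subjects were consented under Amendment 4".

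**The concern.** An instruction about which procedures to perform at Day 60 appears to have become a rule about whom to analyse. That it was carried over from the schedule footnote is an inference; the SAP gives no reason for it. SAP 1 makes the SAP prevail over the protocol on data analysis, so a programmer following sections 2.2.2 and 10.2 would drop non-intubated subjects from Day 60 all-cause mortality and clinical status even though their data are scheduled. The groups compared would then no longer be the randomised groups, because intubation can follow randomisation and is itself one of the listed endpoints.

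**Working it through.** **1. Who is covered at Day 60, by source**

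| Day 60 item | Protocol (synopsis, Table 1, 15.3.3, 19.3) | SAP 13.2 schedule | SAP 2.2.2 and 10.2 |
|---|---|---|---|
| NIAID status | all subjects | no limit | intubated only |
| Oxygen use, ventilation | all subjects | no limit | intubated only |
| Survival | all subjects | no limit | intubated only |
| Discharge | not an endpoint, but NIAID status records hospitalisation in all | as for NIAID status | intubated only |
| Adverse events | all subjects | no limit | intubated only in 2.2.2; not in 10.2 |
| Safety laboratory tests | intubated only | intubated only | intubated only in 2.2.2; not in 10.2 |
| Vital signs, ECG | intubated only | intubated only | not listed as endpoints |

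The sources agree only on the laboratory tests. Among the protocol's own Day 60 endpoints, the laboratory changes are the only group with the limit (synopsis and 19.3). The SAP conflicts with itself as well as with the protocol, so its precedence rule cannot settle the matter.

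**2. If intubated means intubated on Day 60**

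Every analysed subject is alive, in hospital and at score 7 on the SAP 7.8 scale. In both arms:

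- ventilation is 100%;
- oxygen-free, discharged and dead are each 0%;
- improved is 0%, since a one-point gain would need a baseline score of 8, which is death;
- NIAID change is 7 minus baseline, so it reflects baseline alone.

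Nothing is left to compare.

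**3. If intubated has the protocol 15.3.3 meaning (at entry or at any later point)**

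The set is selected at least partly on an event after randomisation. The documents give no intubation rate, so a rate r is assumed, with n = 5 as the largest possible number with a Day 60 visit. The expected number left out is 5(1 − r), and the chance that nobody remains is (1 − r)^5.

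| Assumed r | Expected left out of 5 | Chance nobody remains |
|---|---|---|
| 10% | 4.5 | 0.9^5 = 0.590 |
| 20% | 4.0 | 0.8^5 = 0.328 |
| 30% | 3.5 | 0.7^5 = 0.168 |
| 40% | 3.0 | 0.6^5 = 0.078 |

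**4. Separate point: Day 60 numbers without the limit**

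The SAP appendices give 31 subjects consented under Amendment 2 and 5 under Amendment 4: 31 + 5 = 36, of whom 5/36 = 13.9% can have a Day 60 visit. SAP 10.2 nevertheless requires Pearson chi-square tests for the proportions at one-sided 0.025. When the arms separate completely, the uncorrected statistic equals N, so the one-sided p is ½·P(χ² with 1 df > N). The corresponding one-sided Fisher p is 1 divided by the number of ways to choose one arm from N; it is smallest for the most even split.

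| N | Pearson one-sided p | Smallest Fisher p |
|---|---|---|
| 3 | 0.0416 | 1/3 = 0.333 |
| 4 | 0.0228 | 1/6 = 0.167 |
| 5 | 0.0127 | 1/10 = 0.10 |

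With four or five subjects the planned test can therefore fall below 0.025 where an exact test cannot.

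**The case against.** The strongest reply is that little depends on this. Day 60 involves at most five subjects, and possibly fewer, since some who consented may have failed screening. The endpoints are unadjusted secondaries in a pilot without a power calculation. The planned outputs are already unrestricted: Tables 14.2.3 to 14.2.8 name no intubated subset, SAP 10 promises a listing of all efficacy measurements, and deaths have their own table and listing. The adverse-event limit appears only in SAP 2.2.2. The safety section does not repeat it, and events at Day 60 would normally fall outside the treatment-emergent window of 7 days after the last dose and into the unrestricted post-treatment table. The Day 60 literal reading is also implausible, because mortality among people currently intubated makes no sense, and the protocol supplies a workable definition.

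Most of this stands as a statement about size. It does not remove the contradiction. Unrestricted table titles alongside a restricted analysis section leave the programmer with two incompatible instructions. The protocol's definition avoids the absurd reading but not the selection on a post-randomisation event. The small-sample test figures are a separate matter that the footnote does not cause, and the intubation rates are assumptions.

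**Conclusion.** The concern holds. The SAP's Day 60 limit contradicts the protocol, the SAP's own Amendment 4 schedule and its Full Analysis Set, and it reaches all six Day 60 efficacy endpoints, plus adverse events in SAP 2.2.2. It is right only for the Day 60 laboratory changes. Under one reading the results are fixed by construction. Under the other, at assumed intubation rates of 10% to 40%, on average 4.5 to 3.0 of five subjects are left out, and the chance that none remain runs from 59% to 8%.

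It should be fixed, but the consequence is limited. The Day 7 co-primary endpoints and the Day 28 endpoints are unaffected, deaths remain visible in unrestricted outputs, and five subjects cannot support a Day 60 comparison under either wording. The conclusion about the contradiction rests on the text alone; only the counts in the second reading depend on the assumed rates.

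**What to change.** Remove the intubated-only limit from the Day 60 efficacy, mortality, discharge and adverse-event items in SAP 2.1.2, 2.2.2, 7.8 and 10.2. Replace the footnote with wording to this effect: Day 60 covers subjects randomised under Amendment 4; Day 60 laboratory parameters, vital signs and ECG alone are confined to intubated subjects, as defined in protocol 15.3.3. SAP 10.2 contains no safety laboratory endpoint, so only the first half is needed there.

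Separately, because at most five subjects can contribute, state that Day 60 outcomes will be reported as counts by arm with a listing, and exempt them from the Pearson and ANCOVA tests in SAP 10.2.

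The cost is SAP wording only. The Day 60 data are already scheduled in every Amendment 4 subject.
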